5.1.2.4 Statistical Methods for Secondary Efficacy Objectives

The efficacy profile of the study vaccine candidate was planned to be investigated with collected COVID-19 cases of efficacy endpoint including virologically-confirmed COVID-19-like illness and serologically-confirmed SARS-CoV-2 infection. However, as the development of the mRNA COVID-19 vaccine has been suspended, analyses of correlated of risk and of vaccine efficacy will not be performed.

5.1.3 Statistical Methods for Exploratory Objectives

No hypotheses will be tested.

For descriptive purposes, the statistics presented in [Table 5.1](#) will be produced.

Exploratory Immunogenicity Objectives

Ratio between pseudovirus neutralizing antibody titer and binding antibody (ELISA) concentration will be calculated and provided with 95% CI by study intervention groups. Analyses will be conducted on overall population and by age group.

Last available pseudovirus neutralizing antibody titer and binding antibody (ELISA) concentration before infection will be described with 95% CI in aggregated mRNA vaccine group

and aggregated placebo group among the virologically-confirmed COVID-19-like illness and serologically-confirmed SARS-CoV-2 infection.

Antibodies titers measured using a live virus neutralization assay or other assays and antibody against other emergent variants (eg, B.1.351, B.1.1.7, P.1) might also be summarized in terms of GMTs, fold-rise, and percent of participants with ≥ 2 -fold rise and ≥ 4 -fold rise titers and their corresponding 95% CI at each testing timepoints (D01, D36, and other timepoints), if applicable.

Post-vaccination antibody titers for the different study intervention groups may be compared with human convalescent sera antibody titers, conditional to convalescent sample availability.

T-Cell cytokine profile

For descriptive purposes, the statistics presented in [Table 5.1](#) will be produced for:

- the levels of each cytokine measured at D01, D22, and D36
- the fold-rise of each cytokine measured at D22 and D36 against baseline (D01)
- the Th-1/Th-2 ratios of the fold-rises at D22, D36 against baseline (D01)

Memory B cells

The descriptive statistics presented in [Table 5.1](#) will be produced for the memory B cells measured at D01 (pre-vaccination) and at D112 (post-vaccination), the proportion of antigen-specific ASC, and their fold-rises at D112 relative to D01.

5.2 Analysis Sets

Five main analysis sets were originally defined in the protocol: the PPAS, the Per-Protocol Analysis Set for immunogenicity (PPAS-IAS), the Per-Protocol Analysis Set for AIT (PPAS-AIT), the Full Analysis Set (FAS), and the SafAS. An additional Analysis Set of “modified FAS” is defined in this version of SAP. SafAS1 and SafAS2 will also be used for safety post dose 1 or post dose 2.

5.2.1 Full Analysis Set

Subset of randomized participants who received at least 1 injection of the study intervention. Participants will be analysed according to the intervention group to which they were randomized.

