5.1 Statistical Methods

Safety, immunogenicity, and efficacy analysis will be undertaken including those data collected before the date of receiving an authorized/approved COVID-19 vaccine. Those data collected on or after receiving an authorized/approved COVID-19 vaccine will be listed separately.

For those participants who did not receive an authorized/approved COVID-19 vaccine outside the study, immunogenicity data collected until the last scheduled/unscheduled study visit will be used for analysis. Rules about how to handle unscheduled visit are detailed in Table 5.2. Safety data collected until the last phone contact will be used for analysis if participants did not receive an authorized/approved COVID-19 vaccine outside the study

Safety analyses will be conducted based on two populations: *i*) participants in the Full Enrollment Cohort (Cohort 1 and 2) only, and *ii*) all participants in the Full Enrollment Cohort and Sentinel Cohort, if necessary. Immunogenicity analyses and efficacy analyses will be conducted based on the combined population (Full Enrollment Cohort + Sentinel Cohort) only, in which the same

dose-level group in Sentinel Cohort and Full Enrollment Cohort will be pooled. Subgroup analyses will be performed by age-group.

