5.1.1.2 Statistical Methods for Primary Safety Objective

The following safety parameters will be used for the evaluation of safety. Additional parameters may be displayed as appropriate.

Solicited Reactions

Number and percentage of participants with:

- Presence of solicited injection site reactions and systemic reactions occurring up to 7 days after injection
- Each solicited reaction according to time of onset, maximum intensity, and number of days of occurrence over the solicited period

Unsolicited Events and Reactions

Number and percentage of participants with:

- Any unsolicited immediate systemic event in the 30 minutes after injection
- Any unsolicited event and reaction (using the current MedDRA version) 21 days after injection
- Any unsolicited event/reaction according to time of onset, maximum intensity, and duration

SAEs

Number and percentage of participants with:

- Any SAE within 21 days after injection and throughout the entire study according to SOC and PT, seriousness, and outcome

AESIs

Number and percentage of participants with:

- Any AESI within 21 days after injection and throughout the entire study according to SOC and PT, seriousness, and outcome

MAAEs

Number and percentage of participants with:

- Presence of MAAEs within 21 days after injection and throughout the entire study

Laboratory tests

- Presence of out-of-range biological test results up to 8 days post-last dose (ie, up to D09 for Cohort 1 and up to D30 for Sentinel Cohort and Cohort 2)
- Summary of toxicity grade shift from baseline

For descriptive purposes, the statistics presented in [Table 5.1](#) will be produced for the above safety parameters for each intervention group and each age group. The same dose-level group in Sentinel Cohort and Cohort 2 will also be pooled for analysis.

Harm analysis

Harm analysis assessed based on split of COVID-19 case will be assessed based on Safety Analysis Set (SafAS) at the time of the final analysis. Participants will be analyzed according to the study intervention they received. For the assessment, all dose-level arms will be pooled, and all placebo arms will be pooled as well.

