5.2.2 Safety Analysis Set

The SafAS is defined as subset of randomized participants who have received at least 1 injection of study intervention. All participants will be analyzed after any dose according to the intervention received at the 1st dose.

The SafAS1 and SafAS2 are defined as subsets of randomized participants who have received the 1st or the 2nd injection of study intervention respectively. All participants will be analyzed after each dose according to the intervention they received.

Safety data recorded for a vaccine received out of the protocol design will be excluded from the analysis (and listed separately).

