5.2.4 Other Analysis Sets

Enrolled participants

All participants with a dose-level group that has been allocated by interactive response system (IRT).

Randomized participants

A randomized participant is a participant for whom a randomized group has been allocated by IRT.

Participants with data in CRF

Participants with data in CRF are participants for whom data were recorded at a visit (except screening).

Modified FAS (mFAS)

Subset of FAS that excludes participants with positive pseudovirus neutralization test results against SARS-CoV-2 D614G variant at baseline (D01).

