5.2.5 Populations Used in Analyses

Participants' disposition, demographics, baseline characteristics and exposure will be summarized by planned intervention group for all screened participants or Enrolled participants.

The primary safety analysis will be performed on the SafAS, SafAS1, and SafAS2 by injection group according to the vaccine received.

The primary immunogenicity analyses, the secondary immunogenicity analyses, and the exploratory immunogenicity analyses will be performed on the mFAS by injection group as actually received. This is due to a high rate of protocol deviations and dosing errors found in the preliminary analysis for sentinel cohort.

The secondary efficacy analysis will also be performed on the mFAS by injection group as actually received.

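### SAP 5.2.1 and 5.2.2 define the FAS and the safety sets on randomized participants, which read literally excludes the non-randomized Sentinel Cohort that the SAP's own analyses require

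*SAP*

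**What the plan says.** SAP 5.2.1 gives the FAS as "Subset of randomized participants who received at least 1 injection of the study intervention". SAP 5.2.2 says "The SafAS is defined as subset of randomized participants who have received at least 1 injection of study intervention", and it defines SafAS1 and SafAS2 on randomized participants who received the first or second injection. SAP 5.2.4 then defines the key term: "A randomized participant is a participant for whom a randomized group has been allocated by IRT". The same section defines enrolled participants separately, as those with a dose-level group allocated by IRT, and makes mFAS a subset of FAS.

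Several parts of the SAP need the Sentinel Cohort in these sets:

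- SAP 5.1: "Immunogenicity analyses and efficacy analyses will be conducted based on the combined population (Full Enrollment Cohort + Sentinel Cohort) only".
- SAP 5.2.5 puts the primary and secondary immunogenicity analyses on mFAS, adds that "the exploratory immunogenicity analyses will be performed on the mFAS by injection group as actually received", and puts the efficacy analysis there too. It assigns safety to SafAS, SafAS1 and SafAS2.
- SAP 5.1.1.2, on safety: "The same dose-level group in Sentinel Cohort and Cohort 2 will also be pooled for analysis". SAP 5.1.1.4 has the same pooling for primary immunogenicity.
- SAP 5.1.1.2 runs the harm test on SafAS: "For the assessment, all dose-level arms will be pooled, and all placebo arms will be pooled as well".

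Protocol 9.3 defines both FAS and SafAS on enrolled participants. SAP 5.7 describes the SAP as protocol v3.0 plus the modifications it lists, and a move from enrolled to randomized is not among them.

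**The concern.** Under Protocol 1.1 (Overall Design) and 6.3.1, the Sentinel Cohort is assigned sequentially and only the Full Enrollment Cohort is randomized. The schedules agree. Protocol Table 1.3 (Sentinel) has IRT contacts for participant number and dose number only, while Tables 1.4 and 1.5 (Cohorts 1 and 2) have an IRT contact for randomization. By the SAP's own definitions, Sentinel participants are enrolled but not randomized. The membership rule therefore gives a different population from the one the analyses call for.

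The affected sets carry the primary immunogenicity analysis, all other immunogenicity, efficacy and the safety tables that include Sentinel. Membership flags are programmed from the definition, and a reader who applies it cannot reproduce the denominators of the combined analyses. The harm test is also exposed. It is the one formal hypothesis test the SAP specifies, and its null share is the vaccine fraction of the population. The Sentinel Cohort adds vaccine recipients but no placebo recipients.

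**Working it through.** **Step 1. Reproduce the plan's totals** (Protocol Tables 4.2 and 4.3). Full Enrollment: 2 × (44 + 44 + 44 + 22) = 308. Initial Sentinel: 10 + 5 + 10 = 25. Target: 308 + 25 = 333. Maximum: 308 + 75 = 383. All match Protocol 9.2 and SAP 5.5.

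**Step 2. Apply the definitions.** The Sentinel Cohort has no randomized group allocated, so it is not in FAS, SafAS, SafAS1 or SafAS2. Since mFAS is a subset of FAS, it is not in mFAS either. The combined population in SAP 5.1 would reduce to Full Enrollment alone, and the Sentinel + Cohort 2 pools to Cohort 2 alone. SAP 5.7 reports that mFAS was used at the Sentinel preliminary analysis; under the present wording that set would be empty.

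**Step 3. Share removed, S / (FE + S), on planned sizes.** Each progressing dose level adds 2 × 44 = 88 vaccine recipients, and placebo is 2 × 22 = 44. So FE = 132, 220 or 308 for 1, 2 or 3 levels. Sentinel S = 25 (initial only), 10 + 25 + 10 = 45 (low dose expanded) or 75 (all expanded).

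| Levels | S = 25 | S = 45 | S = 75 |
|---|---|---|---|
| 3 | 25/333 = 7.5% | 45/353 = 12.7% | 75/383 = 19.6% |
| 2 | 25/245 = 10.2% | 45/265 = 17.0% | 75/295 = 25.4% |
| 1 | 25/157 = 15.9% | 45/177 = 25.4% | 75/207 = 36.2% |

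If Full Enrollment is only half filled (154, an assumption), S = 45 gives 45/199 = 22.6%.

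**Step 4. Where the loss falls** (three levels). All Sentinel participants are aged 18-49. That stratum of Full Enrollment is 2 × (3 × 20 + 10) = 140, so the loss there is 25/165 = 15.2%, 45/185 = 24.3% or 75/215 = 34.9%. A fully expanded Sentinel + Cohort 2 dose pool falls from 44 + 25 = 69 to 44 (25/69 = 36.2%). With the initial group only, it falls from 54 to 44 (ultra-low, medium) or from 49 to 44 (low).

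**Step 5. Harm-test null share, vaccine / total.**

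| Levels | Without Sentinel | S = 25 | S = 45 | S = 75 |
|---|---|---|---|---|
| 3 | 264/308 = 0.857 | 289/333 = 0.868 | 309/353 = 0.875 | 339/383 = 0.885 |
| 2 | 176/220 = 0.800 | 201/245 = 0.820 | 221/265 = 0.834 | 251/295 = 0.851 |
| 1 | 88/132 = 0.667 | 113/157 = 0.720 | 133/177 = 0.751 | 163/207 = 0.787 |

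For three levels, take the smallest n with pⁿ ≤ 0.05, that is, every case in a vaccine recipient. It is 20 without Sentinel (0.0458), and 22 (0.0443), 23 (0.0468) or 25 (0.0473) with S = 25, 45 or 75.

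**The case against.** The strongest reply is that nobody would apply the literal wording. SAP 5.1, 5.1.1.2 and 5.1.1.4 name the Sentinel Cohort, 5.2.3 writes a Sentinel-specific exclusion into the PPAS (itself a subset of FAS), and 5.7 links mFAS to Sentinel dosing errors. The protocol also uses randomization language loosely, for example for all participants in its surveillance section (8.2.2.2) and in its own PPAS definition. This stands as evidence of intent, and the shares above describe a reading that the authors did not mean. It does not rescue the rule, because SAP 5.2.4 defines the two terms side by side and 5.2.1 and 5.2.2 choose the wrong one.

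Other points stand in part:

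- S = 25 is a weak lower case. Protocol 6.3.1 says that the low-dose expansion has already been exercised, so 45 is nearer to v3.0. If the medium dose is not reached, S would be 10 + 25 = 35, giving 35/255 = 13.7% with two levels.
- The preliminary analysis preceded this SAP version, so its use of mFAS shows intent and does not prove a conflict with text then in force.
- SAP 1 does announce changes to the populations used in analyses, though not this one.
- Safety population (i) is Full Enrollment only by design and is unaffected; population (ii) applies only if necessary. The pooling in 5.1.1.2 carries no such condition.
- The harm-test question is partly separate. Once the wording is corrected, pooling all dose-level arms most naturally includes Sentinel, so only a clarification is needed. Interaction terms in the optional regressions are also judged at 0.05, so the harm test is not the only use of a significance level.

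**Conclusion.** The concern holds. SAP 5.2.1 and 5.2.2 state a membership rule that, with the definition in 5.2.4, excludes the Sentinel Cohort from every set that the combined and pooled analyses use. It contradicts SAP 5.1, 5.1.1.2, 5.1.1.4 and 5.2.5, departs from Protocol 9.3, and is not listed in 5.7. Inclusion was plainly intended, so the defect is in the written rule; nothing shows that Sentinel data were left out.

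Across the tabulated scenarios, the planned participants removed by a literal application range from 7.5% (three levels, initial Sentinel only) to 36.2% (one level, all groups expanded). These are illustrations on planned arm sizes and the 2:1 ratio. Enrolment was stopped on 27 September 2021 and the documents do not give actual numbers; for a given Sentinel size, the share rises as Full Enrollment falls short. The effect on the harm-test null share is small with three levels (0.857 against 0.868 to 0.885) and larger with one (0.667 against 0.720 to 0.787). This should be fixed, since the rule governs the primary immunogenicity population and the pooled safety tables.

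**What to change.** In SAP 5.2.1 and 5.2.2, replace *randomized participants* with *enrolled participants*, as in Protocol 9.3, for FAS, SafAS, SafAS1 and SafAS2; mFAS then follows.

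In 5.2.1, make the FAS analysis group the one to which the participant was enrolled or assigned, and bring the randomized-to-receive condition in 5.2.3 into line. Both are consistency edits: 5.2.5 analyses mFAS by intervention actually received and assigns PPAS to no analysis.

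In 5.1.1.2, add one sentence saying whether the harm test on SafAS includes the Sentinel Cohort, which has no placebo group.

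If a restriction to randomized participants is deliberate, list it in 5.7 and reconcile 5.1, 5.1.1.2 and 5.1.1.4 with it. The cost is a few words in three sections and one added sentence, with no new data.

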5.2.2 Safety Analysis Set

The SafAS is defined as subset of randomized participants who have received at least 1 injection of study intervention. All participants will be analyzed after any dose according to the intervention received at the 1st dose.

The SafAS1 and SafAS2 are defined as subsets of randomized participants who have received the 1st or the 2nd injection of study intervention respectively. All participants will be analyzed after each dose according to the intervention they received.

Safety data recorded for a vaccine received out of the protocol design will be excluded from the analysis (and listed separately).

5.2.3 Per-Protocol Analysis Set

Subset of the FAS. Participants presenting with at least one of the following conditions will be excluded from the PPAS:

- Participant did not meet all protocol-specified inclusion criteria or met at least one of the protocol-specified exclusion criteria
- Participant did not complete the protocol-defined vaccination schedule
- Participant received a study intervention other than the one that he / she was randomized to receive
- Preparation and / or administration of study intervention was not done as per-protocol
- Participant did not receive study intervention in the proper time window as defined in the protocol visits.
- Participant receives an authorized/approved COVID-19 vaccine prior to D22 (Cohort 1) or D36 (Sentinel Cohort and Cohort 2).
- Participant with positive test results (\geq LLOQ) in the pseudovirus neutralization test* at baseline.

*Only SARS-CoV-2 D614G variant will be considered.

The above conditions leading to exclusion from the PPAS may be detailed and completed if necessary, following the data review. In any case, if PPAS definition is modified, the PPAS definition will be finalized before the database lock and documented in an SAP update.

5.2.3.1 Per-Protocol Analysis Set for Immunogenicity (PPAS-IAS)

Subset of PPAS excluding participants who provided all post-dose serology samples outside the proper time window or no post-dose serology sample was drawn.

For participants with just a few expected post-dose serology samples outside the proper time window or without a valid test result, participants will be kept in PPAS-IAS and only samples within time window and with valid result will be included in immunogenicity analyses.

5.2.3.2 Per-Protocol Analysis Set for AIT subset (PPAS-AIT)

Subset of PPAS excluding participants who provided all post-dose AIT samples outside the proper time window or no post-dose AIT sample was drawn.

5.2.4 Other Analysis Sets

Enrolled participants

All participants with a dose-level group that has been allocated by interactive response system (IRT).

Randomized participants

A randomized participant is a participant for whom a randomized group has been allocated by IRT.

Participants with data in CRF

Participants with data in CRF are participants for whom data were recorded at a visit (except screening).

Modified FAS (mFAS)

Subset of FAS that excludes participants with positive pseudovirus neutralization test results against SARS-CoV-2 D614G variant at baseline (D01).

5.2.5 Populations Used in Analyses

Participants' disposition, demographics, baseline characteristics and exposure will be summarized by planned intervention group for all screened participants or Enrolled participants.

The primary safety analysis will be performed on the SafAS, SafAS1, and SafAS2 by injection group according to the vaccine received.

The primary immunogenicity analyses, the secondary immunogenicity analyses, and the exploratory immunogenicity analyses will be performed on the mFAS by injection group as actually received. This is due to a high rate of protocol deviations and dosing errors found in the preliminary analysis for sentinel cohort.

The secondary efficacy analysis will also be performed on the mFAS by injection group as actually received.

5.3 Handling of Missing Data and Outliers

5.3.1 Safety

Generally, no replacement will be done. However, imputations may be done for a limited number of scenarios, some of which are described in this section.

5.3.1.1 Immediate

Unsolicited systemic AEs with a missing response to the "Immediate" field will be assumed to have occurred within the 30-minute surveillance period.

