**Table 3.1: Objectives and endpoints**

Objectives	Endpoints
Primary	

Safety
 
To describe the safety profile of all participants in each age group and each study intervention group up to 12 months post-last dose.
	
Safety
 
 
• Presence of unsolicited systemic AEs reported in the 30 minutes after each injection
 
• Presence of solicited injection site reactions and systemic reactions (pre-listed in the participant's Diary Card [DC] and Case Report Form [CRF]) occurring up to 7 days after each injection
 
• Presence of unsolicited AEs reported up to 21 days after each injection
 
• Presence of medically attended adverse events (MAAEs) throughout the study
 
• Presence of serious adverse events (SAEs) and adverse events of special interest (AESIs) throughout the study
 
• Presence of out-of-range biological test results up to 8 days post-last dose (ie, up to Day [D] 09 for Cohort 1 and up to D30 for Sentinel Cohort and Cohort 2)
 

Objectives	Endpoints

Immunogenicity
 
To describe the neutralizing antibody profile at D01, D22, and D36 of each study intervention group.
	
Immunogenicity
 
Neutralizing antibody titers against the SARS-CoV-2 D614G variant will be measured with the neutralization assay
 
 
• Antibody titer at D01, D22, and D36
 
• Fold-rise (fold-rise in serum antibody neutralization titer post-vaccination relative to D01) at D22, and D36
 
• 2-fold and 4-fold-rise in serum neutralization titer (post/pre) relative to D01 at D22, and D36
 
• Occurrence of neutralizing antibody seroconversion defined as baseline values below lower limit of quantification (LLOQ) with detectable neutralization titer above assay LLOQ at D22 and D36
 

Secondary	

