### ***Immediate Event/Reaction:***

Immediate events are recorded to capture medically relevant unsolicited systemic AEs (including those related to the study intervention administered) that occur within the first 30 minutes after vaccination.

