4.4.1.2 Unsolicited Adverse Events

Unsolicited AEs include non-serious unsolicited adverse events (AEs), immediate unsolicited AEs, serious adverse events (SAEs), adverse events of special interest (AESIs), and medically-attended adverse events (MAAEs). Analysis for unsolicited AEs only include those AEs collected within 21 days after each injection. SAEs, AESIs, and MAAEs collected out of this range will only be presented in the analysis of SAEs, AESIs, and MAAEs.

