4.4.1.2.4 Time of Onset

Time of onset is derived from the start date of the unsolicited AE provided in the clinical database and the date of last vaccination as described in [Section 4.4.1.2.3](#):

Time of Onset = start date of the unsolicited AE – date of last vaccination before the unsolicited AE + 1

The time of onset should be considered as missing only if one or both of the dates are missing or partially missing.

The unsolicited AEs will be analyzed “Within 21 days”, which corresponds to AEs with a time of onset between 1 and 22 days or missing.

An AE with missing time of onset will be considered to have occurred just after the vaccination indicated by the visit number in “Appeared after visit” or similar filed, so will be included in these tables.

Time of onset will be displayed as follows:

- D01-D04
- D05-D08
- D09-D15
- D16 or later
- Missing

Note: To further clarify the analysis,

- Any unsolicited AEs collected throughout the study (SAEs, MAAEs, or AESIs) with time of onset > 22 days after each injection will not be presented in tables of unsolicited AEs within 21 days but only in tables of SAEs, MAAEs, or AESIs.
- Any unsolicited AEs (planned to report up to 21 days) with time of onset between 1 and 22 days or missing after each injection will be presented in the tables of unsolicited AEs within 21 days.
- Any unsolicited AEs (planned to report up to 21 days) with time of onset > 22 days after each injection will not be presented in any tables but listed separately.
- Any unsolicited AEs with null (0) or negative time of onset will be excluded from the above tables and listed separately.

Main safety analysis will include only those unsolicited AEs with time of onset before a participant received a non-study authorized/approved COVID-19 vaccine if applicable. Events with time of onset on or after the date of receiving a non-study authorized/approved COVID-19 vaccine will be listed separately.

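### SAP 5.3.1.1 counts an unsolicited systemic AE with a blank 'Immediate' field as immediate even when its recorded start date is after the injection day

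*SAP*

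**What the plan says.** The first primary safety endpoint in Protocol Table 3.1 is "Presence of unsolicited systemic AEs reported in the 30 minutes after each injection". Protocol Appendix 10.3.1 defines immediate events as unsolicited systemic AEs "that occur within the first 30 minutes after vaccination". SAP 5.1.1.2 carries the endpoint forward as the number and percentage of participants with "Any unsolicited immediate systemic event in the 30 minutes after injection".

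SAP 5.3.1.1 is a single sentence on missing data for this endpoint: unsolicited systemic AEs with a blank in the 'Immediate' "field will be assumed to have occurred within the 30-minute surveillance period". It attaches no condition.

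Start dates are handled elsewhere. SAP 4.4.1.2.4 states: "Time of onset is derived from the start date of the unsolicited AE provided in the clinical database". The formula is "Time of Onset = start date of the unsolicited AE – date of last vaccination before the unsolicited AE + 1", so the injection day is day 1. The tables cover AEs within 21 days, "which corresponds to AEs with a time of onset between 1 and 22 days or missing". SAP 4.4.1.2 sets the same outer limit: "Analysis for unsolicited AEs only include those AEs collected within 21 days after each injection".

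**The concern.** A worst-case imputation is sensible when nothing is known about timing. Here the SAP may hold a complete start date that rules out the imputed value, and it uses that same date to derive onset day for the same event. Take an AE with a start date giving onset day 12 and a blank field. It would appear under D09-D15 in the onset display and also as an event in the 30 minutes after injection. The two outputs would contradict each other.

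The endpoint is a primary one in a first-in-human study of a novel lipid nanoparticle. If true immediate events are few or absent in a group, one or two such records could make up the whole reported rate.

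**Working it through.** **1. Does any section add a date condition?**

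- SAP 5.3.1.1: none.
- SAP 4.4.1.2.3: compares start date with vaccination dates, but only to decide which injection the AE follows.
- SAP 4.4.1.2.4: derives onset day and does not mention the 'Immediate' field. It lists separately AEs with zero or negative onset, and AEs starting on or after receipt of a non-study COVID-19 vaccine. Neither provision removes an AE with onset day 2 to 22.
- SAP 5.1.1.2: lists the endpoint with no date filter.
- SAP 5.3.1.5: deals only with start and stop dates that are themselves missing or partial.

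The rule therefore stands as written.

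**2. How much of the window conflicts with it?** Onset day = start date − date of last injection + 1. An event within 30 minutes of injection has start date = injection date, hence onset day 1. The tabulated window is days 1 to 22, so 22 − 1 = 21 of the 22 possible onset days contradict an imputed immediate event. The latest such AE starts 21 days after injection.

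**3. What does one misplaced event do?** The plan gives no figure on this point to reproduce. The SAP's interval for a proportion is Clopper-Pearson: lower limit = Beta(0.025; x, n − x + 1), upper limit = Beta(0.975; x + 1, n − x), with lower limit 0 when x = 0. Group sizes are the planned ones in Protocol Table 4.3 (44 per vaccine group, 22 per placebo group). Assume no true immediate events.

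| Misplaced AEs (in different participants) | n = 44 | n = 22 |
|---|---|---|
| 0 | 0% (0 to 8.0%) | 0% (0 to 15.4%) |
| 1 | 2.3% (0.1 to 12.0%) | 4.5% (0.1 to 22.8%) |
| 2 | 4.5% (0.6 to 15.5%) | 9.1% (1.1 to 29.2%) |

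Check on the first cell: 1 − 0.025^(1/44) = 8.0%.

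**4. How likely is it?** The documents give neither the rate of blank fields nor the rate of later-dated systemic AEs. Assume, for illustration only, that a proportion a = 20% to 40% of participants have one unsolicited systemic AE dated after the injection day, and that a proportion m = 1% to 10% of fields are blank, independently. Expected misplaced AEs per 44 = 44 × a × m. Chance of at least one = 1 − (1 − a × m)^44.

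- a = 0.2, m = 0.01: 44 × 0.002 = 0.09 expected; 1 − 0.998^44 = 8%.
- a = 0.2, m = 0.05: 44 × 0.01 = 0.44 expected; 1 − 0.99^44 = 36%.
- a = 0.4, m = 0.10: 44 × 0.04 = 1.76 expected; 1 − 0.96^44 = 83%.

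The span from 8% to 83% shows that the assumptions drive the answer. It is not an estimate for this trial.

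**The case against.** The strongest reply is that this is a deliberate conservative convention, like the treatment of missing causality as related in SAP 5.3.1.2. It can add immediate events but cannot hide one. It may also never operate on a later-dated AE. The CRF and the separate Tables, Listings and Figures document are not available, so the field may be mandatory or shown only for injection-day events. Source data verification (Protocol 10.1.7) and data review before lock (SAP 5.6) would also catch some blanks. The safety analysis is descriptive, and this SAP version serves a final analysis after development was discontinued, so no dose or progression decision depends on the count.

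Most of this stands, and it limits the importance of the point. It does not supply the missing condition. Conservatism justifies filling a gap in information, not overriding a recorded date.

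Three stronger readings are tempting, and the documents do not support them.

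- A reader might infer that any start date qualifies, even that of an SAE months later. SAP 4.4.1.2 names immediate AEs as a category of unsolicited AE and limits the unsolicited analysis to 21 days after each injection. SAP 4.4.1.2 and 4.4.1.2.4 send later SAEs, AESIs and MAAEs only to their own tables.
- A reader might infer that the error falls more on vaccine than on placebo. The rule is the same in every arm, and the documents give neither AE rates nor blank-field rates by arm.
- A reader might infer that the anaphylaxis signal is compromised. Anaphylactic reactions are a protocol-specified AESI (SAP 4.4.1.5.7), and AESIs are tabulated separately under SAP 5.1.1.2.

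**Conclusion.** The point holds in a limited form and should be corrected. Followed literally, SAP 5.3.1.1 gives a wrong classification for any unsolicited systemic AE that has a blank 'Immediate' field and a complete start date 1 to 21 days after the injection. That AE enters a primary safety endpoint whose protocol definition it cannot meet. This is a stated rule that produces a wrong result, not a detail left unstated.

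The size is unknown. One such AE is worth 2.3 percentage points in a group of 44 and raises the upper confidence limit from 8.0% to 12.0%. These are planned group sizes; enrollment was stopped early and the documents do not give the final numbers. The literal reading of 5.3.1.1 is confirmed. How often it changes a count rests on the CRF design and the number of blanks, which cannot be seen here.

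**What to change.** Replace the sentence in SAP 5.3.1.1 with a conditional rule, for example:

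*A missing 'Immediate' response for an unsolicited systemic AE is imputed as immediate only if the AE start date equals an injection date, or if the start date is missing or partial and compatible with an injection date, with the 'Appeared after Visit' field identifying the injection as in Section 4.4.1.2.3. If the start date is complete and later than the injection date, the AE is classified as not immediate. All AEs with an imputed response are listed.*

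The condition should use the recorded start date rather than the derived onset day, because SAP 5.3.1.5 also sets onset to missing when only the stop date is missing.

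The cost is one SAP paragraph, one extra condition in the derivation and one short listing. No new data are needed, since the start date and the visit field are already used in 4.4.1.2.3 and 4.4.1.2.4. The worst-case imputation is kept wherever the date allows it. If no later-dated AE has a blank field, the tables do not change.
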